8.3 Statistical Methods for Testing Superiority

8.3.1 MMRM

Superiority testing will be performed using a mixed model for repeated measures (MMRM) analysis of covariance (ANCOVA) Model.³⁹ The MMRM approach is a direct likelihood approach requiring specialized statistical software. For this study, all MMRM parameters will be estimated using SAS PROC MIXED. The MMRM model is notable for its inclusion of all available data from all eligible subjects and does not require their exclusion as in complete case analysis or arbitrary assignment of some value as in Last Observation Carried Forward (LOCF). Inclusion of outcome data from time points earlier than Months 6 informs the implicit imputation of missing Month 6 values through the covariance matric used to model the random effects.

The random effects in the MMRM model will based on the so-called 'unstructured covariance matrix' in which variances over time are allowed to vary as are the pair-wise correlations over time.

The values over time will include all WOMAC scores, namely at each of the 3 follow-up time points, visit 5 / 2 months, visit 6 / 3 months, and visit 7 / 6 months.

All WOMAC values will be included in the analysis even if they are obtained outof-window. However, the fraction of out-of-window visits will be summarized at each time point.

The contrast indicated by the primary hypotheses above, $\delta(pain)_{ACP} - \delta(pain)_{Control}$ will be estimated as the treatment group contrast from baseline to Month 6 in the WOMAC score derived from the MMRM. The null hypothesis is that the true value of this contrast is equal to zero. The same approach will be taken for the WOMAC Function score if superiority in pain relief is demonstrated.

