8.3.2 Covariates in MMRM

The MMRM model must contain an indicator variable for treatment group, a categorical time factor, and treatment group by time interaction. It is also necessary to include to the baseline value of the WOMAC outcome variable (either pain or function) so that significance levels will apply equally to values over time and to changes from baseline. Often a factor for site is included in the MMRM to account for randomization within site. Given the modest sample size and in

response to FDA Advisory items c.1.b (dated July 23, 2015), site will not be included in the primary MMRM. Instead, the impact of site heterogeneity on estimated treatment group differences will be evaluated in supporting analyses by introducing an additional random effect as described below.

It is often considered useful to include additional baseline covariates in order to further reduction of potential bias due from missing values. Candidate variables include age, gender, BMI, and prior analgesic use. However, in response to FDA Advisory item c.1.b, these variables will not be included in the primary MMRM model. Instead, additional baseline covariates will be added to the model in exploratory analyses only if any of these variables appear with clinically significant imbalance between treatment groups. The purpose of these analyses would to be determine the extent to which such imbalance impacts on estimated treatment group differences and associated significance levels.

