8.3.3 Details Concerning the MMRM

As stated above, the covariance matrix for MMRM is an unstructured covariance matrix in which each of the 3 variances (2 months, 3 months, and 6 months) are free to vary as are the 6 pairwise covariances. That is, the covariance matrix for the MMRM will not inlcude any random effects per se, but accounts for correlations among errors by specifying the form of the covariance matrix. The MMRM employs an unstructured covariance in order to produce inferences that are valid under the so-called 'missing at random' (MAR) assumption which is more generally true than the 'missing completely at random' assumption that is required for validity of analyses restricted to complete cases.

The longitudinal model will be specified as a repeated measures model that expresses the WOMAC score as a linear function of treatment, time, treatment-by-time interaction, and a covariate of the baseline pain measurement.

The model can be mathematically expressed as:

 $Y_i = X_i\beta + e_i$

- Yi is change from baseline to Month 6 in WOMAC Pain or Function scores
- βis a vector of fixed-effect regression parameters which includes:
 - $\circ \mu$, the overall mean
 - \circ θ , the treatment effect
 - \circ τ , a vector of post-baseline time effects
 - \circ **η**, a vector of treatment-by-time interaction effects,
 - $\circ \phi$, a vector of covariate effect parameters that only includes baseline WOMAC score but in general could include additional baseline variable,
- X is a design matrix for the fixed effects, and
- **e** is the error vector with
 - $\circ \quad \mathbf{E}(\mathbf{e}) = \mathbf{0} \text{ and}$

• $Var(e) = \sigma_e^2 V_{unstructured}$.

The specific model to be used may be expressed as:

$$Y = b_{int} + b_{base} + b_T + b_{2M} + b_{3M} + b_{6M} + b_T b_{2M} + b_T b_{3M} + b_T b_{6M}$$

With parameters as explained below.

Parameter	Represents
Y	Change from baseline
b _{int}	Model intercept
b _{base}	Baseline value
b_T	Indicator for Active Treatment
$b_{2M} b_{3M}, b_{6M}$	Indicator for each visit
bтb2м, bтb3м, bтb6м	Indicators allowing varying treatment differences at each visit

From this model estimates of treatment effect at specific visits and specifically at Month 6 difference may be obtained as follows.

 $T_{M6} = b_{int} + b_{base} + b_T + b_T b_{M6}$

 $S_{M6} = b_{int} + b_{base}$

 $\Delta_{M6} = T_{M6} - S_{M6} = b_T + b_T b_{M6}$

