Where e.g. T_{M6} and S_{M6} are the expected changes from baseline to Month 6 in the WOMAC scores in the active and sham control groups, respectively, in terms of these model parameters, the superiority hypotheses are:

H₀: $\Delta_{M6} = 0$ H₁: $\Delta_{M6} > 0$ when larger values reflect improvement or

H₀: $\Delta_{M6} = 0$ H₁: $\Delta_{M6} < 0$ when smaller values reflect improvement

The following SAS Proc Mixed statements provides the test for this null hypothisis. The key results is listed among the results provided by the 'slice' option of the LSMEANS statement. One of these will provide the treatment group contrast at Month 6.

proc mixed data=dataset method=ml;

class patid trt time;

model womac_pain = trt time trt*time womac_pain_bl / s chisq;

repeated time / type=un subject=patid; lsmeans trt*time / slice=time; run;

The Month 6 treatment group contrast, the p-value associated with the null hypotheses and 95% two-sided confidence interval will be derived from the MMRM in order to test the superiority hypotheses for the primary endpoint and co-primary endpoints.

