8.8.6 Treatment of Missing Data

All patients contributing at least one follow-up WOMAC Total score will be included in the primary superiority test through the use of the mixed model for repeated measures (MMRM) in the mITT analysis set. In this way patients with incomplete follow-up are retained and contribute to the primary superiority test.

As noted elsewhere, FDA has previously recommended to not include many baseline covariates in the MMRM due to the modest sample size. Therefore, the only baseline covariates available for implicit imputation of changes from baseline to Month 6 (180 days) is the baseline value itself and treatment group. It follows then, that for the ITT analysis, the MMRM will implicitly impute missing changes from baseline to Month 6

(180 days) for patients with no follow-up data as the within treatment group mean change score modified by the effect of the baseline value

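### The primary MMRM holds the baseline-WOMAC slope equal at Months 2, 3 and 6; a baseline-by-visit term would be a small, nearly free improvement

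*Combined protocol and SAP*

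**What the plan says.** Section 8.3.2 lists the required terms: "The MMRM model must contain an indicator variable for treatment group, a categorical time factor, and treatment group by time interaction". It also requires the baseline value of the outcome. Section 8.3.3 describes a model that "expresses the WOMAC score as a linear function of treatment, time, treatment-by-time interaction, and a covariate of the baseline pain measurement", writes an equation with a single baseline coefficient, and codes it as "model womac_pain = trt time trt*time womac_pain_bl / s chisq". The outcomes modelled are those at "visit 5 / 2 months, visit 6 / 3 months, and visit 7 / 6 months" (8.3.1), with an unstructured covariance.

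Text, equation and code therefore agree: only treatment interacts with time. It makes no difference that the equation uses change and the code uses the score. A common slope on one scale is a common slope on the other, and the treatment contrast is the same.

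No supporting analysis frees the slope. The ITT and complete-case tests in 8.8.1 reuse the same MMRM. The exploratory models in 8.3.2 add other baseline variables, and 8.8.5 concerns site.

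On missing data, 8.3.3 says: "The MMRM employs an unstructured covariance in order to produce inferences that are valid under the so-called 'missing at random' (MAR) assumption". On model size, 8.8.6 says: "FDA has previously recommended to not include many baseline covariates in the MMRM due to the modest sample size".

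**The concern.** The estimand is the Month 6 contrast, so the baseline adjustment that matters is the Month 6 slope. The plan estimates a slope pooled over three visits. If the relation between screening pain and later pain weakens over time, the pooled slope is steeper than the Month 6 slope. Two things could follow.

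- **Precision.** Some Month 6 variation that baseline could explain is left in, or over-corrected.
- **Bias under MAR.** Likelihood-based validity under MAR needs the mean model to be right as well as the covariance. With a wrong slope, a baseline imbalance among the patients still observed at Month 6 is adjusted by the wrong amount.

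The advice on model size does not settle this. As 8.3.2 describes it, that advice concerns site and additional covariates such as age, gender, BMI and prior analgesic use. Baseline WOMAC is already in the model, and letting its slope vary adds no new covariate.

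**Working it through.** **1. The plan's own figures.** Section 8.4.1 uses effect size 0.80, one-sided alpha 0.025 and 2:1 allocation. Two-sample t-test power is 0.908 at 52/26 and 0.897 at 50/25, so N = 78 reproduces; 78 × 1.15 = 89.7, rounded to 90. The design effect is 0.80 × 3.4 = 2.72 points.

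**2. How strong is the baseline relation?** The pilot baseline SDs in 8.4.1 are 1.8 and 2.0 (about 1.9), and the planning SD is 3.4, applied to follow-up and to change. With follow-up SD 3.4:

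- Var(change) = 3.4² + 1.9² − 2ρ(3.4)(1.9). Setting this equal to 3.4² gives ρ = 1.9/(2 × 3.4) = 0.28.
- Month 6 slope = 0.28 × 3.4/1.9 = 0.50; variance explained = 0.28² ≈ 8%.

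Section 8.4.1 also mentions a correlation of 0.5 between baseline and change, but only as a condition for using SD 3.4. No document gives a correlation by visit, so every fading pattern below is an assumption.

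**3. Precision.** Simulated trials of 60/30 (600 per pattern), ML with unstructured covariance. Assumed: baseline SD 1.9, residual SD 3.2–3.26, residual correlations 0.6–0.7, effect −2.7. Mean model-based Month 6 SE, common slope / visit-specific slopes:

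| Slopes at Months 2/3/6 | Complete data | Ratio | Dropout on last pain, mainly in controls | Ratio |
|---|---|---|---|---|
| 0.5/0.5/0.5 | 0.7152/0.7152 | 1.000 | 0.7549/0.7548 | 1.000 |
| 0.7/0.6/0.5 | 0.7194/0.7181 | 1.002 | 0.7570/0.7549 | 1.003 |
| 1/0.75/0.5 | 0.7278/0.7187 | 1.013 | 0.7633/0.7511 | 1.016 |
| 0.8/0.6/0.3 | 0.7284/0.7189 | 1.013 | 0.7702/0.7559 | 1.019 |
| 1/0.5/0 (extreme) | 0.7555/0.7205 | 1.049 | 0.8043/0.7550 | 1.065 |

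Specified by correlation instead (follow-up SD 3.4, follow-up correlations 0.70/0.55/0.65, complete data), separate runs give SE ratios of 1.007–1.009 for baseline correlations 0.50/0.45/0.30 and 1.030–1.036 for 0.60/0.50/0.25. The ratio is 1.001 for 0.30/0.30/0.20 and 0.999 for a constant 0.40. A 3% variance loss moves normal-approximation power at N = 78 from 0.915 to 0.907.

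**4. Bias.** Roughly, shift ≈ −(pooled slope − Month 6 slope) × (baseline difference, ACP minus control, among patients observed at Month 6). Randomisation makes the second factor zero on average with complete data, so fading alone gives no bias. Large-sample fits (40,000/20,000 patients), common minus visit-specific, in points (negative favours ACP):

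| Slopes | Baseline-dependent, same rule in both arms | Last pain, same rule in both arms | Last pain, mainly controls | High-baseline controls selectively |
|---|---|---|---|---|
| 0.7/0.6/0.5 | +0.002 | −0.001 | −0.014 | −0.064 |
| 1/0.75/0.5 | −0.002 | −0.019 | −0.051 | −0.155 |
| 0.8/0.6/0.3 | −0.004 | −0.004 | −0.038 | −0.170 |
| 1/0.5/0 (extreme) | −0.022 | −0.030 | −0.075 | −0.293 |

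Month 6 missingness is 8–14% on ACP and 13–24% on control; in the last column it is 8% and 23–24%. The rough formula fits that column: for 0.8/0.6/0.3 the slope error is 0.60 − 0.30 = 0.30, and 0.170/0.30 ≈ 0.57 points of baseline imbalance; for 0.7/0.6/0.5 it is 0.064/(0.61 − 0.49) ≈ 0.53.

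At trial size under similar selective dropout (8% on ACP, about 20% rising with baseline pain on control), with a true contrast of −2.72:

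- Correlations 0.50/0.45/0.30: common slope −2.84, visit-specific −2.75, shift 0.09.
- Correlations 0.60/0.50/0.25: −2.91 and −2.74, shift 0.17.
- Weaker patterns: 0.03 for 0.35/0.32/0.28 and 0.05 for 0.40/0.35/0.28.

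**5. Scale.** 0.17/0.73 = 0.23 SE, and 0.17/2.72 = 6% of the design effect. With no true effect, a shift of 0.09–0.17 at SE 0.73 would raise one-sided error from 0.025 to 1 − Φ(1.96 − 0.12) ≈ 0.033 and 1 − Φ(1.96 − 0.23) ≈ 0.042. That requires fading and arm-specific selective dropout together.

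**The case against.** The case for leaving the model alone is largely sound on size.

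- **A common slope is valid for the randomised contrast with complete data.** This stands. A reader might infer that a fading baseline relation by itself biases the result; the calculations show that it does not.
- **Fading is not documented.** A reader might infer that the shared slope is too steep for Month 6. The documents do not show this: they give no correlations by visit, and all three modelled visits fall after the last injection at Week 2. This stands.
- **The larger shifts rest on one adverse dropout rule.** Section 8.4.1 gives only an overall 15% allowance. Selective loss of high-pain controls is conceivable: non-acetaminophen analgesics are barred for six months (3.8), and pilot controls improved only from 10.5 to 9.1 (8.4.1). That is plausibility, not evidence.
- **Section 8.8.6 does not show that the primary test depends on this slope.** Its statement that missing changes are imputed "as the within treatment group mean change score modified by the effect of the baseline value" is tempting to cite. It describes the supporting ITT analysis for patients with no follow-up. The primary mITT test requires at least one post-randomisation WOMAC, and missing Month 6 values there also draw on Months 2 and 3.
- **The change is not just an edit.** Section 9.16 requires FDA and IRB approval of amendments. This stands.

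What the objection does not supply is a reason for the restriction. The plan gives none, and no planned analysis would reveal whether it matters.

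**Conclusion.** The restriction is real and appears consistently in text, equation and code. Its likely effect is small. The Month 6 SE is about 0–1% larger under mild to moderate fading and about 3–4% larger under strong fading, with somewhat more only if the slope vanishes by Month 6. The contrast shifts by about 0.03–0.17 points towards ACP only when the slope fades and high-baseline controls also drop out selectively. That is at most about a quarter of a Month 6 SE of 0.73–0.79; the extreme pattern, slope falling from 1 to 0, reaches 0.29. With complete data or symmetric baseline-dependent dropout the shift is about 0–0.02.

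These figures rest on assumed slopes, follow-up correlations and dropout rules; only the SDs and sample sizes come from the documents. It would go too far to conclude that the primary analysis is biased or that its MAR claim has been shown to fail. Low severity: a nearly free improvement, worth making mainly because in these scenarios the possible shift favours the superiority claim.

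**What to change.** Add the term `womac_pain_bl*time` to the MODEL statement of the primary Pain analysis, keeping the existing terms, and add the matching baseline-Function-by-time term for the conditional analysis. In 8.3.3, replace the single baseline coefficient with one for each visit, and list the interaction among the required terms in 8.3.2. The Month 6 slice still gives the treatment contrast, because baseline does not interact with treatment.

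The cost is two degrees of freedom per model, with no new data and no new covariate. There is no measurable SE penalty if the slopes are constant (SE ratio 0.999–1.000 in the simulations). The change needs a protocol amendment under 9.16, so it is best bundled with other changes and fixed before unblinding. If the primary model is to stay as it is, pre-specify the baseline-by-visit model as a sensitivity analysis.

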8.4 Sample Size Analysis

8.4.1 Primary Superiority Test

The power for the MMRM tests were approximated by the power for the corresponding two-sample t-test using industry standard software.⁴⁰ Power for the t-test is a function of the magnitude of the treatment group difference relative to the standard deviation of change scores. Preliminary data to evaluate clinical effect size was available from the safety and efficacy pilot study (BB-IDE 14796). In 15 patients per group, the mean (SD) WOMAC Pain Total score for the ACP and control groups at 6 months post-treatment were 2.5 (3.6) and 9.1(3.2) respectively. At screening, the baseline mean (SD) values were 10.2 (1.8) and 10.5 (2.0). Therefore, the large difference at Month 6 is not explainable by baseline differences. These data imply a treatment group difference in mean improvements equal [10.2-2.5=7.7] minus [10.5-9.1=1.4] = 6.3 in favor of ACP and a standard deviation of approximately equal to 3.4. This standard deviation also applies to change from baseline if the correlation between baseline and change scores is equal to 0.5. Given the small sample size of the pilot study, a 95% two-sided confidence interval for the true difference was determined to be (-9.0 to -4.2) in order to account for the uncertainty in estimated treatment group mean differences. Specifically, on the basis of the pilot study, a superiority treatment group differences as small as -4.2 cannot be statistically ruled out. Therefore, as -4.2 represents a conservative estimate of the treatment group difference for purpose of sample size analysis. Under these assumptions, the standardized mean difference (Cohen's effect size) is equal to 1.235. This effect size is typically considered very large. Cohen's benchmark for a large effect size in the behavioral sciences is 0.80. In order to mitigate against any potential bias present in the preliminary study, the expected effect size is further reduced from 1.235 to 0.80. From another perspective, a treatment group difference of -4.2 in mean improvements is clinically significant as follows. The mean WOMAC Pain prior to surgery is slightly more than 10 (range 0 to 20). Therefore, a treatment group difference of -4.2 in the mean improvement in WOMAC Pain score represents about a 40% treatment group difference in the mean percent improvements. A group difference

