in mean percentage changes so large is likely clinically significant given the known reliability and validity of the WOMAC Pain score.

Randomization will be 2:1 in order to increase precision when characterizing the safety profile of the investigational treatment. We assume a one-sided type 1 error of α =0.025 and a standardized mean difference of 0.80 and determined that a total sample size of N=78 (52 ACP and 26 control) patients are required for 90% power. **This value is increased by 15% to N=90 (60 ACP and 30 control)** to account for potential loss-to-follow-up or other exclusions from the primary effectiveness analysis set.

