8.8.4 Description of Effectiveness Outcome

WOMAC Pain, Function, Stiffness, and Total scores and the as well as change scores will be summarized at each planned follow-up visit [Pre-Op, 1 Week, 2 Weeks, 2 Months (60 days), 3 Months (90 days), 6 Months (180 days), and 12 Months (365 days)] using means, standard deviations, medians, minimum, and maximum values. Standardized effect sizes (mean difference divided by the standard deviation of differences) will be computed at each time point for each continuous measure in order to facilitate assessment of group differences across measures as well as time. Pooled t-tests and Wilcoxon rank sum tests will be provided as additional descriptive measures. There will be no imputation of missing values for secondary endpoint and exploratory endpoints and no control for type I error in the set of exploratory endpoints. Graphical displays of selected endpoints will be provided to provide visual assessments of group differences over time.

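### With 2:1 allocation, the primary MMRM's single covariance matrix gives a biased standard error if the arms' true SDs differ; allowing arm-specific variances is a cheap safeguard of low severity

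*Combined protocol and SAP*

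**What the plan says.** Section 8.3.3 gives the SAS code for the success test. Estimation is by maximum likelihood ("proc mixed data=dataset method=ml") and the covariance is set by "repeated time / type=un subject=patid". There is no `group=trt` option and no empirical (robust) standard error option. The text of the section describes a matrix in which "each of the 3 variances (2 months, 3 months, and 6 months) are free to vary"; nothing lets the variances differ by arm. The Month 6 contrast, its p-value and its 95% confidence interval all come from this model.

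Section 8.4.1 sets the allocation and gives a safety reason for it: "Randomization will be 2:1 in order to increase precision when characterizing the safety profile of the investigational treatment". It plans 60 ACP and 30 control patients. The same section reports the pilot WOMAC Pain means (SDs) for ACP and control: "at 6 months post-treatment were 2.5 (3.6) and 9.1(3.2) respectively", from 15 patients per group.

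For the visit-by-visit summaries, section 8.8.4 states: "Pooled t-tests and Wilcoxon rank sum tests will be provided as additional descriptive measures". No planned analysis allows the variance to differ between arms.

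**The concern.** A shared variance does little harm when the arms are the same size. At 60 v 30 the pooled variance takes 59/88 = 67% of its weight from ACP. The variance of the difference, at equal SDs, takes (1/30)/(1/60 + 1/30) = 67% of its size from control. The weights run in opposite directions, so if the true SDs differ the pooled standard error is off. It is too large if ACP is the more variable arm, which costs power. It is too small if control is, which makes the confidence interval too narrow.

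Study success rests on one p-value from this model, at one-sided 0.025, and the conditional Function test uses the same model. The plan neither relaxes the equal-variance assumption nor checks it.

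**Working it through.** **Plan's own figure.** Section 8.4.1 states: "We assume a one-sided type 1 error of α =0.025 and a standardized mean difference of 0.80". The effect size comes from a deliberate discount: "the expected effect size is further reduced from 1.235 to 0.80". With 52 and 26 patients, the noncentrality is 0.80 × √(52 × 26/78) = 3.33 on 76 df. Power is 90.8%, against 89.7% at 50/25, so N = 78 reproduces. 78 × 1.15 = 89.7, hence 90. This calculation assumes a common SD.

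**Formulas.** For arm sizes n₁ (ACP) and n₂ (control):
- Pooled: s²ₚ = [(n₁−1)s₁² + (n₂−1)s₂²]/(n₁+n₂−2), and SE = √[s²ₚ(1/n₁ + 1/n₂)]
- True: SE = √(s₁²/n₁ + s₂²/n₂)

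**Pilot Pain SDs (ACP 3.6, control 3.2) at 60/30.**
- s²ₚ = (59 × 12.96 + 29 × 10.24)/88 = 12.06; pooled SE = √(12.06 × 0.05) = 0.777
- True SE = √(12.96/60 + 10.24/30) = 0.747
- Ratio 1.040: the pooled SE is 4% too large.

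**The same SDs reversed (an assumption).**
- s²ₚ = (59 × 10.24 + 29 × 12.96)/88 = 11.14; pooled SE = 0.746
- True SE = √(10.24/60 + 12.96/30) = 0.776
- Ratio 0.961: the pooled SE is 4% too small.

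**Simulated one-sided error for equal means, 60/30, nominal 0.025.** This is the complete-data t-test analogue of the Month 6 contrast, with 160,000 runs.

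| SDs (ACP, control) | Pooled | Welch |
|---|---|---|
| 3.4, 3.4 | 0.025 | 0.024 |
| 3.6, 3.2 (pilot Pain) | 0.021 | 0.025 |
| 3.2, 3.6 (reversed) | 0.029 | 0.025 |
| 11.7, 12.0 (pilot Function, section 8.4.2) | 0.026 | 0.025 |
| 3.4, 4.25 (assumed ratio 1.25) | 0.034 | 0.025 |

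Separate runs at the reversed SDs gave 0.030. For Function the SE ratio is 0.992.

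**Power at 0.80 × 3.4 = 2.72 points.** With the pilot SDs at 52/26, power is 90.6% pooled and 91.6% Welch. With equal SDs it is 90.9% pooled and 90.5% Welch.

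**Do the pilot SDs show a difference?** The variance ratio is 12.96/10.24 = 1.27. On F(14,14) the two-sided p is 0.67, and the 95% interval for the SD ratio is 0.65 to 1.94.

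**Three-visit MMRM at 60/30.** This used complete data, 8,000 runs, an assumed between-visit correlation of 0.6, an assumed baseline correlation of 0.3 and 87 df. The simulation error is about 0.002.

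| SDs (ACP, control) | One matrix, ML (plan) | Arm-specific, ML | Arm-specific, approximate REML |
|---|---|---|---|
| 3.6, 3.2 | 0.020 | 0.027 | 0.025 |
| 3.4, 3.4 | 0.028 | 0.029 | 0.027 |
| 3.2, 3.6 | 0.034 | 0.030 | 0.027 |

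A further MMRM simulation with dropout, again with assumed correlations, gave 95% interval coverage of about 0.95 in both SD orders for arm-specific REML with Welch-type df. The plan's model gave about 0.935 when control was the more variable arm.

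**The case against.** A common covariance matrix is the conventional MMRM specification, and the plan keeps its primary model small on purpose: section 8.3.2 cites the modest sample size and FDA advice. That advice concerns covariates rather than the covariance matrix, but the case for parsimony carries over, because a second matrix would rest on 30 controls or fewer.

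A reader might infer from the pilot that the SDs are known to differ. The documents do not support that. The difference is well within chance, the figures are raw Month 6 scores rather than the baseline-adjusted residuals that the MMRM uses, and for Function the order reverses and the gap almost closes.

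A reader might also infer that the success test has an inflated false-positive rate. The Pain pilot points the other way, to a conservative test. A treatment that helps some patients and not others would most naturally widen the ACP arm, which is again the conservative direction. The rates of about 0.030 and 0.034 need a more variable control arm together with equal means, and nothing in the Pain data suggests that.

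Finally, the t-tests in 8.8.4 are labelled descriptive and do not decide study success. All of this stands and sets the low severity. It does not remove the point that the standard error depends on an assumption that the plan never tests and that 2:1 allocation makes matter more.

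**Conclusion.** This is a small, cheap improvement and not a demonstrated error. The structural facts are clear: one matrix for both arms, 2:1 allocation, and no analysis that relaxes equal variances. The size of any bias depends on the unknown true SDs. At differences like the pilot's it is about 4% of the standard error in either direction.

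If ACP has no effect at all and the SDs are therefore equal, sharing the matrix does not affect type 1 error. The benefit lies in a correct confidence interval, and in power when ACP is the more variable arm.

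The t-test figures assume complete, normally distributed data. The MMRM figures also rest on correlations that the documents do not give. The slight excess under ML at equal SDs is a separate matter from sharing the matrix, but it bears on how the change should be made.

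**What to change.** Add `group=trt` to the REPEATED statement, change the method to REML, and name Satterthwaite or Kenward-Roger degrees of freedom. These belong together, because arm-specific matrices under ML did not bring the error back to nominal in the simulation. If a second matrix is thought too much for the primary model at this sample size, the minimum is to prespecify the same analysis, or robust standard errors, as a sensitivity analysis of the primary test. In 8.8.4, replace the pooled t-tests with Welch tests and keep their descriptive status.

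The cost is a wording and code change before unblinding, six more covariance parameters (three variances and three covariances for the second arm), and about 0.2 to 0.5 percentage points of power if the SDs are equal. N stays at 90.
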